## SECTION 4: STUDY INTERVENTION ADMINISTRATION OF DATA COLLECTION

*NIE* is a mixed methods study involving quantitative and qualitative methodology. There are four data collection components to *NIE*: 1) student survey (quantitative); 2) parent survey (quantitative); 3) systems level tracking (qualitative); and 4) fidelity, acceptability and sustainability evaluation (qualitative). The student survey, parent survey and systems level tracking data collection are described in section 4.1. The fidelity, acceptability and sustainability evaluation data collection is described in section 4.2.

**4.1. *NIE* Intervention Components:** The intervention components and corresponding modes of data collection to test efficacy of the four aspects of our intervention are shown in the table below. The left column indicates the intervention component, while the right column indicates the type of data collection and the timeline of data collection.

Intervention Component	Types of Data Collection and Timeline
Individual level: Native Stand	
 
• Student Surveys: baseline, 3 months, 9 months, 12 months
 

Family level: Native Voices	
 
• Parent Surveys: baseline, 9 months, 12 months
 

Community level: Cultural Mentoring	
Systems level: Enhancement of the coordination and implementation of SRH services at Fort with the Fort Peck Epi Team	
 
• Barriers and Facilitators Discussion Group: yearly
 
• Coordination & Implementing Monitoring Plan Tracking Log: quarterly
 

Subsequent to randomization of the 5 area schools to the intervention, there will be a baseline data collection from the middle of March to June 2019, followed by three waves of implementation and concurrent data collection over the next 3 years. For a visual picture of how these intervention components and methods of data collection fit into an overall Timeline, please see our Trial Timeline in the appendix.

**For the student and parent/legal guardian participating in *NIE*, there are 2 forms of data collection:** a student survey and a parent/legal guardian survey. [name], a part-time assistant, and the N/E school outreach coordinator will oversee both surveys' administration. The student surveys and parent/legal guardian surveys will be completed using Research Electronic Data Capture or "REDCap." REDCap is a secure web application for building and managing surveys and databases.

The students and parents will take the survey on iPads that have the mobile application version of REDCap installed on the tablets. The mobile app version of REDCap collects data offline to be uploaded to an online, secure database once a secure wifi location is reached. Deidentified data will be stored virtually on the REDCap server and available for download to [name], [name], [name], [name] and [name]. Only [name], the *NIE* outreach coordinator, and [name] will have access to names linking students and parents to their records during data collection and intervention implementation. These files will be kept in a locked file cabinet by [name] at MSU after data collection.

From Years 2-4, 456 students and one of their parents/legal guardians will participate in *NIE*'s data collection. Student surveys for baseline, 3, and 9 months will be administered during regularly scheduled classes in an assigned classroom by [name], the assistant, and N/E's outreach coordinator. Baseline data collection will begin in March 2019 for all schools and parents included in the intervention. Groups of 20 students at a time will be appropriately spaced in the classroom in order to ensure privacy, and survey instructions will be presented to students prior to REDCap administration. [name], the assistant, and the *NIE* outreach coordinator will thoroughly review the assent form with the students, which will include a description of *NIE*, types of questions that will be asked, and potential risks and benefits of participating in *NIE*. All students will be reminded that they can withdraw at any time without consequences. Prior similar procedures have been successfully used by [name] and [name] for data collection in the Fort Peck schools with AI youth. For students who graduate from high school prior to the 12-month follow-up, they and their parent/legal guardian will be contacted by [name] to complete the 12-month follow-up (during evening hours) at the high school from which they graduated following the same procedure described above. Although data collection for the students has been designed to coincide with the school year, the same procedures will be followed if the data collection occurs when school is not in session.

Wave 1 data collection will commence in December 2019 with 1 school after students have begun receiving the Native Stand and Cultural Mentoring components of the intervention during the school year.

Wave 1 9- month follow-up will take place at the end of the school year in May/June 2020 as the intervention is completed. The Wave 1 12-month follow-up will take place at the beginning of the next school year in September 2020.

Wave 2 (2 schools) and Wave 3 (schools) will follow the same procedures and pattern of timeline of data collection. The parent survey will be administered during evening hours at the high school by [name], the assistant, and N/E's outreach coordinator. All baseline parent data will be collected in Fall 2019. We will use the same REDCap administration procedures for parents/legal guardians that are described for students above. [name], the assistant, and the N/E outreach coordinator will review the consent forms with the parents/legal guardians to ensure their understanding of the purpose of N/E, types of questions they will be asked, and the study's potential risks and benefits. All parents/legal guardians will be reminded that they can withdraw themselves and/or their child at any time without consequences.

Wave 1 (parents of first school) parent 9- month follow up will take place in spring of 2020. Wave 1 parent 12-month follow-up will take place in Fall 2020. Wave 2 (parents of schools 2 and 3) and Wave 3 (parents of schools 4 and 5) will follow the same procedures and pattern of timeline of data collection. Data Safety & Monitoring Plan describes participant safety and support plans

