#### **B.6 WHAT DO YOU PLAN TO DO DURING THE NEXT REPORTING PERIOD TO ACCOMPLISH THE GOALS?**

The following will be completed during the next reporting cycle (12/01/18 to 11/30/19):

- \* Implement baseline data collection in the 5 schools at Fort Peck between 3/01/19 to 6/01/19.
- \* Begin implementation of Aim 2 to test the efficacy of NIE for 15- to 18-year-old AI youth. Implementation of NE will begin in 9/2019 in one school at Fort Peck. The first school to receive NE in 9/2019 has yet to be determined because, as outlined in our proposal and in keeping with our study's Stepped Wedge Design, we must collect baseline data first and then randomize the schools into the intervention.
- Implement systems level component of NE.
- \* Manage data software REDCap.
- \* Convene DMSP committee and 2 hold meetings.
- \* Hold 4 community advisory board meetings and meet with community advisory board members individually as needed.

The following accomplishments have been completed during reporting period (4/01/18 -11/30/18) related to the study's specific aims (goals):

**AIM 1.** Refine, tailor, and finalize the components of *NIE*. Our community advisory board and the Fort Peck-based and MSU-based research team will design culturally appropriate adaptations for *NIE*'s 4 levels during the first year of the study, based on the analysis of our recently completed qualitative and quantitative research (focus groups, interviews, and surveys), as well as discussions with elders and community stakeholders.

- 3 community advisory board meetings have been held to refine, tailor and finalize the components of *NIE*, including Native Stand, Native Voices, the Cultural Mentoring Program, and the System's Level adaptations.
- 4 meetings have been held specifically with [name], [name] and [name] to discuss the integration of the Cultural Mentoring Program with Native Stand and Native Voices.
- 2 meetings have been held with members of the Fort Peck Epi Team to discuss the adaptation of reproductive health services for 15-18 year old tribal youth.
- 2 discussions have been held with elders to talk about *NIE*.
- Subawards have been established with Fort Peck Community College, the Fort Peck Tribes Language and Culture Department, and Northern Arizona University.
- 3 meetings (2 conference calls and 1 in-person) with [name] at Northern Arizona University who is [name] senior research mentor on the study, to discuss tailoring of *NIE*.

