5.3 During your life, with how many people have you had sexual intercourse?

- a. 1 person
- b. 2 people
- c. 3 people
- d. 4 people
- e. 5 people
- f. 6 or more people

5.4 During the past month, how many people have you had sex with? \_\_\_\_\_ [# of people]

5.5 During the past month, how many TIMES have you had sex? \_\_\_\_\_ times

5.6 Of the times you had sex over the past month, how many TIMES was a condom used?  
\_\_\_\_\_ times

5.7 Of the times you had sex over the past month, how many TIMES did you use birth control other than a condom, like birth control pills or having a deprova shot?  
\_\_\_\_\_ times

Over the past month, did you drink alcohol or take any kind of drug and have sex? Yes No

5.9 Did you drink alcohol or use drugs before you had sexual intercourse the **last** time?

- a. I have never had sexual intercourse
- b. Yes
- c. No

5.10 The last time you had sexual intercourse, what one method did you or the person you had sex with use to prevent pregnancy? (Select only one response.)

- a. No method was used to prevent pregnancy
- b. Birth control pills
- c. Condoms
- d. An IUD (such as Mirena or ParaGard) or implant (such as Implanon or Nexplanon)
- e. A shot (such as Depo-Provera), patch (such as OrthoEvra), or birth control ring (such as NuvaRing)
- f. Withdrawal or some other method
- g. Not sure

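### In the 12-month-versus-baseline contrast every untreated survey falls in spring and every treated one in September, so season is aliased with treatment and past-month recall may reach into the summer break

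*Combined protocol and SAP*

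**What the plan says.** **Timing of the student surveys (Section 4.1).** For all five schools, "there will be a baseline data collection from the middle of March to June 2019". The grant progress report (B.6) agrees: "Implement baseline data collection in the 5 schools at Fort Peck between 3/01/19 to 6/01/19". For the first school, "Wave 1 data collection will commence in December 2019 with 1 school", then "Wave 1 9- month follow-up will take place at the end of the school year in May/June 2020", and then "The Wave 1 12-month follow-up will take place at the beginning of the next school year in September 2020". The student surveys in Waves 2 and 3 "will follow the same procedures and pattern of timeline of data collection"; no dates are printed for them.

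**Outcome.** Both parts of the primary outcome use the same short recall (student survey, items 5.5 and 5.6): "During the past month, how many TIMES have you had sex", and "Of the times you had sex over the past month, how many TIMES was a condom used".

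**Primary time point.** Section 3.1.1 states power for the change from baseline to 12 months. Hypothesis H1 in the registration text assigns 12 months to the primary analysis and 3 and 9 months to the secondary ones. The Outcome Measures list in the same registration gives all three visits as the primary time frame.

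**Who is surveyed when.** Section 2.3.5 has one baseline in every school. After that, a school is surveyed only after its students have started the intervention. The section says that the stepped wedge controls for time. The model under the heading on generalized linear mixed-effects models has a fixed effect for time period and one intervention term, and no season term.

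**The concern.** Condom use over a single past month can plausibly differ between school term and the summer break, because partners, number of acts and access to condoms may differ. Season can also change who is evaluable, since a student with no past-month sex yields no ratio. If the untreated measurement is always taken in one season and the treated measurement always in another, any such difference enters the 12-month estimate one for one and is read as an effect of the programme. It could flatter or hide a true effect. A reader may also assume that the period effect deals with this, because the protocol says that the design controls for time.

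**Working it through.** **1. The plan's own figure.** From Section 3.1.1: uncorrected size 292, design effect 1.3273, attrition 15%.
292 × 1.3273 = 387.57; 387.57 / 0.85 = 455.97, rounded up to 456. The stated sample size reproduces.

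**2. Season against treatment.**

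| Student survey | Timing | Treated? |
|---|---|---|
| Baseline, all schools | mid-March to June 2019 | no |
| 3 months, Wave 1 | December 2019 | yes |
| 9 months, Wave 1 | May/June 2020 | yes |
| 12 months, Wave 1 | September 2020 | yes |

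With Waves 2 and 3 on the same pattern, the 12-month-versus-baseline contrast has 5 schools × 2 surveys = 10 school-by-period cells. Five are spring and untreated, five are September and treated. An indicator for September equals the treatment indicator in all 10.

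**3. Can the period effect separate them?** Assume the waves are one school year apart. There are then 1 + 3 × 3 = 10 calendar periods, and the fixed part of the model has an intercept, 9 period dummies and treatment (0/1):
- Planned schedule, calendar periods: 11 columns, rank 10.
- Planned schedule, survey occasion (0, 3, 9, 12 months) in place of calendar period: 5 columns, rank 4.
- If waiting schools were also surveyed untreated in each earlier follow-up period: 11 columns, rank 11.

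In the planned schedule the later-period dummies add up to the treatment column. That does not depend on the spacing of the waves, only on there being no untreated survey after baseline. Coding treatment as dose breaks the exact identity, but only by comparing treated students who attended more with those who attended less, and it still supplies no untreated September.

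**4. How much of the recall falls in August.** The documents give no term dates. Assume term starts on 1 September and a 30-day look-back. For a survey on day d of September the August share is (30 − (d − 1))/30:
- 5 September: 26/30 = 87%
- 15 September: 16/30 = 53%
- 25 September: 6/30 = 20%
- averaged over the month: about 52%

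**5. Size, as an illustration.** Taking the power statement at face value and assuming a two-sided test (sidedness is not stated), SE = 0.14/(1.960 + 0.842) = 0.0500. For an assumed seasonal shift s:
- false-positive rate with no true effect = P(Z > 1.96 − s/SE) + P(Z < −1.96 − s/SE)
- power when the shift opposes a true 0.14 = Φ((0.14 − s)/SE − 1.96)

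| s | share of 0.14 | false-positive rate | power |
|---|---|---|---|
| 0 | 0% | 5% | 80% |
| 0.03 | 21% | 9% | 60% |
| 0.05 | 36% | 17% | 44% |
| 0.07 | 50% | 29% | 29% |

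**6. Baseline labels.** Section 2.3.5 puts the baseline in Q4 of Year 2; the recruitment text under Section 6.4.1 puts it in Q2 of Year 2. If Year 2 is the reporting cycle in progress report B.6 (1 December 2018 to 30 November 2019), Q2 is March to May 2019, which broadly fits Section 4.1, and Q4 is September to November 2019, which does not.

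**7. Would agreement in direction with 9 months be a useful check?** Suppose there is no true effect and no shift at 9 months, but a shift of 0.05 (one SE) at 12 months. Among falsely significant positive 12-month results, the 9-month estimate is also positive 50% of the time if the two are independent. At an assumed correlation of 0.5, the mean excess of the 12-month estimate over its expectation is about 1.49 SE, and Φ(0.5 × 1.49/0.866) is about 0.80. Such a rule would let most false positives through.

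**The case against.** - **Season is not a separate problem.** A reader might infer that season is distinct from calendar time and that no model for time could remove it. The documents do not support that. The plan has period effects, and with untreated surveys in the same periods these would absorb a September shift common to all schools (rank 11 of 11 above). The obstacle is that all time after baseline is treated time. This stands: season is one component of that aliasing, and matching season does not cure it.
- **The 9-month data are not ignored.** H1 already tests 9 months as a secondary analysis, and the registration's outcome list puts it in the primary time frame. This stands. What is missing is its role as the season-matched comparison.
- **The written model is not restricted to 12 months.** Fitted to all follow-ups, treated observations fall in December, May/June and September, and season no longer coincides with treatment: spring/December/September indicators plus treatment have full rank (4 of 4). This stands for a pooled analysis. But the plan has no season term, two of its three follow-ups would still be off-season, and both H1 and the power statement point to 12 months.
- **Summer recall is not certain.** It would be too strong to say that every 12-month report describes the summer break. That depends on the day of the survey and on term dates, and September is inferred for Waves 2 and 3.
- **No seasonal effect is documented.** A ratio of condom uses to acts need not move because acts increase. This stands, and it limits what can be said about size.

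**Conclusion.** The point holds in limited form. In the 12-month-versus-baseline contrast, season coincides with treatment in every school, and the planned period effect cannot separate them because no school is surveyed untreated after baseline. This rests on the Section 4.1 dates, on Waves 2 and 3 keeping Wave 1's pattern, and on 12 months being the primary time point. If the Q4 label in Section 2.3.5 were right and meant autumn 2019, the spring-to-September gap would largely disappear, although the aliasing with calendar time would remain.

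Recall lies mostly in August only for a survey in about the first half of September with term starting about 1 September. The wording about the beginning of the school year fits that reading but does not fix it.

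The size and direction of any shift are unknown. The 17% false-positive rate and 44% power are what an assumed shift of 0.05 would do. They are not estimates of bias in this trial, and the documents do not support reading them so.

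**What to change.** 1. **Section 4.1, student data collection.** Open the 12-month survey about a month into the autumn term in every wave, and print the planned month for Waves 2 and 3. The past month then falls in term, as it does at baseline. The cost is that the survey comes about 13 months after the start. A spring-versus-autumn difference remains.
2. **Section 3, analysis plan.** Report the already planned 9-month (May/June) versus spring-baseline estimate with its confidence interval beside the 12-month result, labelled as the season-matched comparison. State that it shares the baseline and is still confounded with calendar time: for Wave 1 it compares spring 2019 with May/June 2020, and the study later obtained approval to examine the impact of COVID-19 on its primary outcomes and design. State too that a difference between the two may be decay after the programme ends rather than season. Do not use agreement in direction as a pass/fail rule. The cost is wording only, since these data are already to be collected.
3. **Reconcile the dates and time frames.** Align the quarter labels in Section 2.3.5 and in the recruitment text under Section 6.4.1 with Section 4.1, and the registration's primary time frame with H1.

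None of this removes the wider aliasing of calendar time with treatment, which needs its own remedy. Untreated surveys of waiting schools in the same periods would make the treatment effect estimable alongside the period effects, at the cost of additional survey rounds.

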be developed based on the multi-level components derived from the Ecological Systems Theory model

upon with the N/E was built. CFAs and SEMs will be conducted using Mplus software.

**3.1.5 Randomization of schools.** The 5 schools that AI youth from Fort Peck attend are the clusters to be randomized into the intervention, with all schools eventually being randomized to the intervention. Students and their parents/legal guardians will be recruited for baseline participation prior to randomization of the sites. Schools will be randomized to the intervention following baseline data collection using a single sequence random assignment to clusters that will determine order of intervention receipt.

**3.1.5 Generalized linear mixed-effects models.** To test for effectiveness of the *NIE* intervention across all hypotheses under Aim 2, the generalized linear mixed-effects models (GLMM) will be used to model binary primary and secondary outcomes (condom use under H1, condom use and other sexual risks under H2) and continuous tertiary outcomes (H3) in the data. The GLMM allows for individual-level binary and continuous responses to be modeled, key covariates to be controlled for, the specification of autocorrelation within individuals, and clustering by school. The GLMM is also the most frequently employed analytic method to adjust for the longitudinal nature of SWDs, and it was chosen over the Generalized Estimating Equations (GEEs) because GEEs show inflated Type 1 error rates when the number of clusters is small, as is the case with the number of schools at Fort Peck. Hussey and Hughes proposed a mixed-effects regression approach for the SWD-CRT design, where:

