## **SECTION 5: SELECTION AND ENROLLMENT OF PARTICIPANTS**

**4.1 Inclusion Criteria.** To be eligible for inclusion in *N/E*, students must be: 1) 15 to 18 years old; 2) a registered member of a federally recognized tribe or an associate tribal member; and 3) a resident of Fort Peck with a parent/legal guardian. For inclusion in the systems-level component of *N/E*, only those staff members who sit on the Epi Team as representatives of their respective agencies are eligible. Written informed consent will be obtained from the head of each agency represented on the Epi Team and the staff member participating in the Epi Team.

**4.2 Exclusion Criteria.** Exclusion criteria are minimal due to the CAB's value of inclusion in *N/E*. Exclusion criteria include: 1) not meeting the aforementioned inclusion criteria; and 2) having a medically identified physical or cognitive impairment that would impede their understanding of and participation in the educational content and activities of *Native Stand*, *Native Voices*, and the cultural mentoring program.

**4.3 Study Enrollment Procedures.** Students and their parent/legal guardian will be recruited from each of the study's 5 schools. Based on discussions with school personnel and our previously successful recruitment strategies, recruitment will occur via flyers posted in the schools, letters to the parents, parent-teacher meetings, and word of mouth. Additionally, a parent/legal guardian session that provides an overview of *N/E*, the content and format of the intervention components, and risks and benefits of participation will be held at each of the study's 5 schools. Students and their parents/legal guardians, and students from each cluster, will be recruited for participation at baseline. Students and their parents/legal guardians will be recruited for baseline participation **prior to randomization of the sites**. Students and parents/legal guardians will be assigned unique study identification numbers. No persons who refuse to participate in the study, in whole or in part, will be coerced to engage in any study activity. After written consent and assent is obtained from the parent/legal guardian and child, respectively, they will be enrolled in the study.

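### The parent baseline is dated Fall 2019, which conflicts with the spring 2019 baseline before randomisation and, for the Wave 1 school, falls largely or wholly after the intervention has begun

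*Combined protocol and SAP*

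**What the plan says.** Section 4.1 dates the parent baseline in two ways. On the parent survey it says: "All baseline parent data will be collected in Fall 2019". A little earlier, on survey administration, it says: "Baseline data collection will begin in March 2019 for all schools and parents included in the intervention". The opening of the section gives the window: "there will be a baseline data collection from the middle of March to June 2019".

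The order of baseline and randomisation also differs between sections. Section 3.1.5 (Randomization of schools) says: "Schools will be randomized to the intervention following baseline data collection using a single sequence random assignment to clusters". Section 2.3.5 (Trial Design) defines the first observation as one at which no cluster has yet been randomised. Section 4.1 opens with the reverse order: "Subsequent to randomization of the 5 area schools to the intervention, there will be a baseline data collection".

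On recruitment, Section 3.1.5 says: "Students and their parents/legal guardians will be recruited for baseline participation prior to randomization of the sites". The enrolment procedures in Section 5 repeat that parents are recruited "prior to randomization of the sites".

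For the start of Wave 1, item B.6 of the appended progress report says: "Implementation of NE will begin in 9/2019 in one school at Fort Peck". Item G.10.c of that report gives 1 September 2019, with randomisation on completion of baseline.

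**The concern.** A baseline in a stepped-wedge trial should be taken before a cluster crosses over, and preferably before anyone can know the order. If the parent survey is first given in Fall 2019, the Wave 1 parents' record carries a baseline label but is taken while their children are receiving the programme.

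Two features make this matter for the analysis. First, the mixed model in Section 3 codes the intervention term by school and period as 0, 1 or a dose, and no rule says which value a Fall 2019 Wave 1 parent record takes. If it is coded 0, exposed data enter the control condition. Second, the topic list in the parent survey asks whether each topic has ever been discussed. A conversation prompted by the programme before the survey becomes a baseline yes and can no longer register as change. If the programme does increase communication, both features pull the Wave 1 parent effect toward zero.

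**Working it through.** There is no stated figure to reproduce. The check is on dates and order.

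**1. Can the dates be reconciled?** A baseline that begins in March could run on into the autumn. But the Fall 2019 sentence covers all parent baseline data, so it leaves none for March to June. The two statements cannot both hold for parents.

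**2. When does Wave 1 start?** The progress report gives September 2019. The Wave 1 student follow-up dates in Section 4.1 agree:
- First follow-up, December 2019, less 3 months = September 2019.
- 9-month follow-up, May/June 2020, less 9 months = August/September 2019.
- 12-month follow-up, September 2020, less 12 months = September 2019.

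**3. Is Fall 2019 after randomisation?** The Wave 1 school must be chosen before it starts, so at least one school has been drawn by 1 September 2019. Section 4.1's reversed order also puts a Fall survey after randomisation. If instead randomisation waited for a Fall parent baseline, as Section 3.1.5 would require, it would come at or after the Wave 1 start, which is not workable.

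**4. How much of Fall falls after the Wave 1 start?** The documents do not define Fall, so three assumed windows are compared with a 1 September 2019 start. Share = days on or after the start ÷ days in the window.

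| Assumed meaning of Fall 2019 | Days after start ÷ total | Share | Weeks from start |
|---|---|---|---|
| 1 Sep to 30 Nov | 91 ÷ 91 | 100% | 0 to 12.9 |
| 23 Sep to 21 Dec | 90 ÷ 90 | 100% | 3.1 to 15.9 |
| School term, about 20 Aug to 20 Dec | 111 ÷ 123 | 90% | -1.7 to 15.7 |

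By contrast, a baseline ending between 1 and 30 June 2019 closes 92 to 63 days before the start, or about 3.0 to 2.1 months at 30.4 days per month.

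**5. What happens to the follow-up interval?** Section 4.1 places the Wave 1 parent 9-month survey in spring 2020. Taking Fall as 1 September to 21 December and spring as 20 March to 15 June (assumed limits):
- Shortest: 21 December to 20 March = 90 days ÷ 30.4 = 3.0 months.
- Longest: 1 September to 15 June = 288 days ÷ 30.4 = 9.5 months.

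**6. Does the conflict appear elsewhere?** Section 2.3.5 places the first observation in Q4 of Year 2, and Section 6.4.1 places recruitment at baseline in Q2 of Year 2. If Year 2 is the progress report's cycle of 1 December 2018 to 30 November 2019 (an assumption), these are September to November and March to May 2019, which is the same split.

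**The case against.** The strongest reply is that Fall 2019 may be deliberate. Section 4.1 gives parents a coherent schedule of their own (Fall 2019, spring 2020, Fall 2020), and on the Year 2 assumption above, Section 2.3.5's quarter fits it. This stands as a reason not to treat the sentence as a slip. It does not remove the conflict with the March 2019 sentence, or with baseline before randomisation. A deliberate Fall date would also still need a coding rule for Wave 1.

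Four stronger readings are tempting, and the documents do not support them:
- **That parents at all five schools know their school's place in the order.** Section 3.1.5 describes a single draw of the sequence. But the aims and Section 2.3.5 describe schools randomised one at a time at successive steps, and the registration record speaks of later groups being randomised in 2019-2020 and 2020-2021. Parents in Waves 2 and 3 may know only that they are not first, and nothing says when schools or parents are told.
- **That Wave 1 parents have already attended Native Voices.** No calendar date is given for its first session, and Section 4.1 names only Native Stand and Cultural Mentoring as under way by December 2019. Exposure through the child is likely; direct exposure is possible but not shown. A survey in early September would carry little of either.
- **That the plan twice says parents are surveyed before randomisation.** Those two sentences concern recruitment. The timing point rests on the March 2019 sentence, the rule that randomisation follows baseline data collection, and the definition of the first observation.
- **That H3 as a whole, or the primary result, is biased.** Table 2 collects the communication scale from students as well, and this sentence does not move the student baseline.

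The planned model also estimates an exposure effect across periods and not simple change from baseline, so any bias depends on how the Wave 1 record is coded. That is accepted, and it is why the coding rule is part of the fix.

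**Conclusion.** The concern holds as a conflict of dates with a limited analytic consequence. Followed as written, the Fall 2019 sentence yields a parent baseline taken after at least the first school has been chosen. For the Wave 1 school, 1 of 5, that baseline falls largely or wholly (about 90% to 100% of the window) after the intervention starts. Contamination within a school is established for Wave 1 only: no text shows a Wave 2 or Wave 3 school starting before a Fall 2019 survey.

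The consequence is confined to the parent-reported part of a tertiary outcome. The size of the bias cannot be computed. It depends on how much communication has changed by the survey date, on the coding of the record, and on Wave 1's share of parents, none of which the documents give. The result rests on a 1 September 2019 start, which comes from the progress report and agrees with the protocol's follow-up dates, and on the assumed meanings of Fall. The plan should be corrected, but the trial's main conclusion does not depend on it.

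**What to change.** 1. Reconcile the statements in Section 4.1 to one parent baseline window that precedes randomisation, as Sections 2.3.5 and 3.1.5 and the March 2019 sentence already intend. Give the parent survey at the baseline consent contact: Section 5 requires written parental consent before enrolment, and Section 7 has staff review consent forms with parents at baseline.
2. Correct the opening of Section 4.1 so that randomisation follows baseline. This is a separate inconsistency, but the window cannot be stated clearly while it remains.
3. In the parent H3 model, code any parent record first collected after that school's start date as exposed (X = 1 or the dose received), not as control or baseline. Record the actual survey date for each parent.

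The date change is not free. Section 4.1 pairs the consent review with the evening parent survey, and Section 6.4.1 ties parental consent to the period before Native Voices, so some parents may need an evening session in spring 2019. The coding rule needs only analysis work, but Wave 1 parents first surveyed late then contribute no pre-intervention record. Appended review-board memoranda are dated April and September 2020, so the spring 2019 window may already have passed. In that case the coding rule and disclosure of the actual dates are what remain.
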